4.1 Description of study design

Patients treated with curative intent either in the post-operative or definitive setting with high dose radiotherapy (≥ 50 Gy) with or without chemotherapy will be eligible. There will be one treatment group with each patient serving as their own control. Patients would have their salivary output measured before radiotherapy, 3 weeks after the start of radiotherapy, and at the end of radiotherapy (6 weeks). Patients who demonstrate more than a 50% decrease in

saliva flow rates will enter the treatment phase of the trial. Based on expert experience, we estimate that half the treated patients will exhibit a decrease of 50% or more in flow rate. These affected patients will then receive the planned dose of everolimus **once a day for 5 days, starting two weeks after the completion of radiotherapy**. Salivary output measurements will be obtained prior to everolimus administration and at completion of the 5 day everolimus course and at 1 month, 3 months and 6 months after the completion of radiation or chemoradiation therapy.

It is our expectation that because of the short exposure to everolimus (a total of 5 days only), the well described everolimus related toxicities will not develop.

However, following discussions with the company (Novartis), two dose levels will be evaluated: a starting dose of 5 mg po daily, will initially be evaluated in a cohort of 3 patients.

For the purpose of this trial, dose-limiting toxicity (DLT) is defined as an everolimus-related grade 3 or higher AE.

Toxicity will be graded based on the Common Terminology Criteria for Adverse Events (CTCAE) Version4.03.

(<http://www.hrc.govt.nz/sites/default/files/CTCAE%20manual%20-%20DMCC.pdf>)

As mentioned, we will start treating enrolled patients on the lower dose level.

-If no DLT occurs, will proceed with dose escalation to the full FDA-approved dose (10 mg po daily) [in this case, total number of patients in the trial: 13; 3 in the 5 mg cohort, 10 in the 10 mg cohort].

-If 1 DLT occurs, cohort will be expanded to additional 3 patients; and if another DLT occurs in this expanded cohort, no escalation to full dose (10 mg po daily) will be attempted, and cohort will be expanded to 10 patients [in this case, total number of patients in the trial: 10; all in the 5 mg cohort];

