6.2.1.2 Dosing modifications

For patients who do not tolerate the protocol-specified dosing schedule, dose adjustments are not permitted.

Table 6-1 and Table 6-2 list the dosing guidelines for Everolimus-related non-hematologic and hematologic toxicities.

Management of severe or intolerable adverse drug reactions (ADRs) may require temporary dose interruption of Afinitor therapy.

The proceeding sections summarize recommendations for dose interruption, or discontinuation of Afinitor in the management of ADRs. General management recommendations are also provided as applicable. Clinical judgment of the treating physician should guide the management plan of each patient based on individual benefit/risk assessment.

Table 6-1 Dosing guidelines for Everolimus-related non-hematologic toxicities

Toxicity	Action
Non-Infectious Pneumonitis	Discontinue Everolimus.
Reactivation of HBV or HCV flare	Discontinue Everolimus.
AST or ALT elevation Grade 1 ($>$ ULN - 3.0 x ULN)	Maintain current dose level
Grade 2 ($>$ 3.0 - 5.0 x ULN)	
AST or ALT elevation Grade 3 ($>$ 5.0 - 20.0 ULN)*	Discontinue Everolimus
AST or ALT elevation Grade 4 ($>$ 20 x ULN)*	Discontinue Everolimus
Intolerable grade 2 mucositis, or grade 3 AE, except hyperglycemia or hypertriglyceridemia or hypercholesterolemia (see Section 6.2.3.8)	Discontinue Everolimus
Any other grade 4	Discontinue Everolimus
Grade 3 or 4 clinical liver failure (asterixis or encephalopathy/coma)	Discontinue Everolimus

* Should HCV flare be confirmed, the guidelines for flare must take precedence (Table 6-6)

Table 6-2 Dosing guidelines for Everolimus-related hematologic toxicities

Toxicity	Action
Grade 2 thrombocytopenia (platelets $<$ 75, \geq 50 x10 ⁹ /L)	No action
Grade 3 thrombocytopenia (platelets $<$ 50, \geq 25 x10 ⁹ /L)	Discontinue Everolimus
Grade 4 thrombocytopenia (platelets $<$ 25 x10 ⁹ /L)	Discontinue Everolimus
Grade 3 neutropenia or anemia (neutrophil $<$ 1, \geq 0.5 x10 ⁹ /L)	Discontinue Everolimus
Grade 4 neutropenia or anemia	Discontinue Everolimus
Febrile neutropenia	Discontinue Everolimus

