6.2.2.6 Management of stomatitis / oral mucositis / mouth ulcers

Adverse Drug Reaction	Severity	Afinitor Dose Adjustment and Management Recommendations
Stomatitis	Grade 1 (Minimal symptoms, normal diet)	No dose adjustment required. Manage with non-alcoholic or salt water (0.9%) mouth wash several times a day.
	Grade 2 (Symptomatic but can eat and swallow modified diet)	Temporary dose interruption until recovery to grade ≤ 1 . Re-initiate Afinitor at the same dose. If stomatitis recurs at grade 2, discontinue Afinitor. Manage with topical analgesic mouth treatments (e.g. benzocaine, butyl aminobenzoate, tetracaine hydrochloride, menthol or phenol) with or without topical corticosteroids (i.e. triamcinolone oral paste)*.
	Grade 3 (Symptomatic and unable to adequately eat or hydrate orally)	Discontinue Everolimus
	Grade 4 (Symptoms associated with life-threatening consequences)	Discontinue Afinitor and treat with appropriate medical therapy.

* using agents containing alcohol, hydrogen peroxide, iodine, and thyme derivatives in management of stomatitis as they may worsen mouth ulcers.

Patients with a clinical history of stomatitis/mucositis/mouth ulcers and those with gastrointestinal morbidity associated with mouth/dental infections, irritation of esophageal mucosa e.g. gastroesophageal reflux disease (GERD) and pre-existing stomatitis/mucositis must be monitored even more closely. Patients should be instructed to report the first onset of buccal mucosa irritation/reddening to their study physician immediately.

Stomatitis/oral mucositis/mouth ulcers due to Everolimus should be treated using local supportive care. Please note that investigators in earlier trials have described the oral toxicities associated with Everolimus as mouth ulcers, rather than mucositis or stomatitis. If your examination reveals mouth ulcers rather than a more general inflammation of the mouth, please classify the adverse event as such. The suggested paradigm for treatment of stomatitis/oral mucositis/mouth ulcers is as follows:

1. For mild toxicity (grade 1), no dose adjustment required. Manage with non-alcoholic mouth wash or salt water (0.9%) mouth wash several times a day until resolution.

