6.2.2.8 Management of hyperlipidemia and hyperglycemia

Adverse Drug Reaction	Severity	Afinitor Dose Adjustment and Management Recommendations
Metabolic events (e.g. hyperglycemia, dyslipidemia)	Grade 1	No dose adjustment required. Initiate appropriate medical therapy and monitor.
	Grade 2	No dose adjustment required. Manage with appropriate medical therapy and monitor.
	Grade 3	Discontinue Everolimus
	Grade 4	Discontinue Everolimus

Treatment of hyperlipidemia should take into account the pre-treatment status and dietary habits of the patient. Grade 2 or higher hypercholesterolemia (>300 mg/dL or 7.75 mmol/L) or grade 2 hypertriglyceridemia or higher (>2.5 x upper normal limit) should be treated with a 3-hydroxy-3-methyl-glutaryl (HMG)-CoA reductase inhibitor (e.g. atorvastatin, pravastatin, fluvastatin) or appropriate triglyceride-lowering medication, in addition to diet.

Note: Concomitant therapy with fibrates and an HMG-CoA reductase inhibitor is associated with an increased risk of a rare but serious skeletal muscle toxicity manifested by rhabdomyolysis, markedly elevated creatine phosphokinase (CPK) levels and myoglobinuria, acute renal failure and sometimes death. The risk versus benefit of using this therapy should be determined for individual patients based on their risk of cardiovascular complications of hyperlipidemia.

Dyslipidemia (including hypercholesterolemia and hypertriglyceridemia) has been reported in patients taking everolimus. Monitoring of blood cholesterol and triglycerides prior to the start of everolimus therapy and periodically thereafter as well as management with appropriate medical therapy is recommended.

Hyperglycemia has been reported in patients taking everolimus. Monitoring of fasting serum glucose is recommended prior to the start of Everolimus and periodically thereafter. More frequent monitoring is recommended when everolimus is co-administered with other drugs that

may induce hyperglycemia. Optimal glycemic control should be achieved before starting a patient on Everolimus.

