8.1 Adverse events

8.1.1 Definitions and reporting

An adverse event is defined as the appearance of (or worsening of any pre-existing) undesirable sign(s), symptom(s), or medical condition(s) that occur after patient's signed informed consent has been obtained.

Abnormal laboratory values or test results occurring after informed consent constitute adverse events only if they induce clinical signs or symptoms, are considered clinically significant, require therapy

(e.g., hematologic abnormality that requires transfusion or hematological stem cell support), or require changes in study medication(s).

Adverse events that begin or worsen after informed consent should be recorded *in the Adverse Events CRF*. Conditions that were already present at the time of informed consent should be recorded *in the Medical History page of the patient's CRF*. Adverse event monitoring should be continued for at least 30 days (or 5 half-lives, whichever is longer) following the last dose of study treatment. Adverse events (including lab abnormalities that constitute AEs) should be described using a diagnosis whenever possible, rather than individual underlying signs and symptoms. When a clear diagnosis cannot be identified, each sign or symptom should be reported as a separate Adverse Event. Adverse events will be assessed according to the Common Terminology Criteria for Adverse Events (CTCAE) version 4.0.

If CTCAE grading does not exist for an adverse event, the severity of mild, moderate, severe, and life-threatening, corresponding to Grades 1 - 4, will be used.

The occurrence of adverse events should be sought by non-directive questioning of the patient (subject) during the screening process after signing informed consent and at each visit during the study. Adverse events also may be detected when they are volunteered by the patient (subject) during the screening process or between visits, or through physical examination, laboratory test, or other assessments. As far as possible, each adverse event should be evaluated to determine:

1. The severity grade (CTCAE Grade 1-4)
2. *Its duration (Start and end dates) (add or Ongoing at End of Study for)*
3. *Its relationship to the study treatment (Reasonable possibility that AE is related: No, Yes or*
Its relationship to the study treatment (Reasonable possibility that AE is related: No, Yes, investigational treatment, Yes, the study treatment (non-investigational), Yes, both and/or indistinguishable)

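### Table 6-1 does not agree with Sections 6.2.2.8 and 6.2.2.6 on stopping everolimus for grade 3 metabolic events and intolerable grade 2 mucositis, and its cross-reference leads nowhere

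*Protocol*

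**What the plan says.** Three places in the protocol set the action for these toxicities.

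- **Section 6.2.1.2, Table 6-1.** One row, whose action is to stop everolimus, covers intolerable grade 2 mucositis together with a "grade 3 AE, except hyperglycemia or hypertriglyceridemia or hypercholesterolemia (see Section 6.2.3.8"). A later row, "Any other grade 4", also stops the drug.
- **Section 6.2.2.8.** The table entry for "Metabolic events (e.g. hyperglycemia, dyslipidemia") requires no dose change at grades 1 and 2, with medical therapy, and stops everolimus at grades 3 and 4. The text below it directs treatment of cholesterol or triglyceride elevations from grade 2 upward.
- **Section 6.2.2.6.** For grade 2 stomatitis the drug is held until recovery to grade 1 or lower and then restarted at the same dose. Only then comes: "If stomatitis recurs at grade 2, discontinue Afinitor". Grades 3 and 4 stop the drug.

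Two definitions matter for the consequences. In Section 4.1, "dose-limiting toxicity (DLT) is defined as an everolimus-related grade 3 or higher AE". In Section 8.1.1, abnormal laboratory values "constitute adverse events only if they induce clinical signs or symptoms, are considered clinically significant, require therapy", "or require changes in study medication(s").

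**The concern.** A dosing table should lead to one action for each toxicity and grade. Here a clinician with a grade 3 glucose or lipid value finds it taken out of the stop row, follows the reference, and finds no such section. A clinician who opens Section 6.2.2.8 directly is told to stop. For grade 2 mucositis that the patient cannot tolerate, one page says stop and another says hold and restart.

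What is at stake is consistent handling of patients at the two facilities named in Section 5, and the number of the five planned doses that a patient receives. Mucositis is no marginal event in this trial. Patients have just finished head and neck radiotherapy, Section 4.1 singles it out as an important comorbidity, and stomatitis heads the list of common oncology adverse reactions in Section 8.1.1.

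**Working it through.** No figure in the plan is in dispute, so the check is mainly a comparison of texts.

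**Step 1: where the reference points.** Section 6.2 contains 6.2.1 and 6.2.2, and the next section is 6.3, so there is no 6.2.3. Section 5.1 makes the same slip twice: it cites 6.2.3.10 for hepatitis management, which stands at 6.2.2.10. Applying the same shift, 6.2.3.8 becomes "6.2.2.8 Management of hyperlipidemia and hyperglycemia", and the subject matches.

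**Step 2: the actions side by side.**

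| Event | Table 6-1 | Toxicity section |
|---|---|---|
| Glucose or lipids, grade 3 | Excepted from the stop row; no other action stated | 6.2.2.8: stop |
| Glucose or lipids, grade 4 | Stop | 6.2.2.8: stop |
| Mucositis, grade 2, intolerable | Stop | 6.2.2.6: hold, restart at same dose, stop on recurrence |
| Mucositis, grade 3 | Stop | 6.2.2.6: stop |

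The mismatches are in the first and third rows.

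**Step 3: can the metabolic exception be read consistently?** If the reference means 6.2.2.8, the exception leads to the action it exempts from and has no effect. If the exception means that grade 3 metabolic events do not automatically stop the drug, it contradicts 6.2.2.8. The exception cannot have an effect and also agree with 6.2.2.8.

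**Step 4: when could a metabolic value meet the conflict?** Table 7-1 schedules biochemistry and lipids at visit 4 (day 15 after radiotherapy) and visit 5 (day 22), each within 1 day, with none in between. Assume that dosing starts at visit 4.

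- Last dose: day 15 + 4 = 19, with a range of 18 to 20.
- Visit 5: days 21 to 23.

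The scheduled post-dose laboratory test comes after the last dose, when there is nothing left to stop. The metabolic conflict therefore needs an unscheduled test during the five dosing days. Such tests are plausible in patients with diabetes or impaired fasting glucose, whom Section 5.1 admits under close glucose monitoring. The mucositis conflict needs no laboratory test: it arises from symptoms, which Section 6.2.2.6 tells patients to report at once.

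**Step 5: does the dosing action change the toxicity count?** A dose-limiting toxicity depends on relatedness and grade, not on whether the drug is stopped. The dosing action can enter only through the last trigger in Section 8.1.1, a required change in study medication. Need for therapy is a separate trigger, and Section 8.1.2 confirms that a laboratory value needing a hold or medication is an adverse event. Section 6.2.2.8 directs therapy for lipids from grade 2 and for metabolic events in general from grade 1. A related grade 3 value treated in that way counts under either reading. Grade 2 mucositis is below grade 3 and cannot count at all.

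**Step 6: the plan's own totals.** The escalation paths are:

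- no toxicity in the first three: 3 + 10 = 13 patients
- one in three, then none in the next three: 6 + 10 = 16
- one in three, then another in the next three: 10
- two in the first three: 10

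The stated range of 10 to 16 is reproduced.

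**The case against.** The strongest case on the other side has four parts.

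- **The exception is merely redundant.** Table 6-1 states no rival action for the excepted events, the numbering slip is systematic, and the only action written for grade 3 metabolic events is the one in 6.2.2.8. This stands as a formal reading, and it is why the texts cannot be called two fully stated opposite rules. It does not make the row harmless. An exception placed inside a stop row tells the user that stopping is not automatic, and the reference that should settle the matter is dead.
- **Intolerable grade 2 mucositis is a special case, and 6.2.2.6 is the default.** The reading is possible, but 6.2.2.6 covers all of grade 2 and does not refer to Table 6-1. Here both actions are written out, so the redundancy argument does not help.
- **These are guidelines.** Section 6.2.1.2 leaves room for clinical judgment, and Section 11.2 provides weekly calls on adverse events and cohort management. These reduce the practical risk, but they do not tell a site which page to follow when the event occurs.
- **The metabolic conflict will be rare.** Given the laboratory schedule, this stands for glucose and lipids. It does not apply to mucositis.

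**Conclusion.** The inconsistency is in the text. For grade 3 hyperglycemia, hypertriglyceridemia and hypercholesterolemia, Table 6-1 holds an exception that is either without effect or contrary to Section 6.2.2.8. For intolerable grade 2 mucositis, Table 6-1 and Section 6.2.2.6 prescribe different actions. The section number is wrong. This should be corrected because it concerns when patients stop treatment. It affects no sample-size or precision figure.

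A reader might go further and infer that the conflict changes the number of dose-limiting toxicities, and so whether 10 mg opens. The documents do not support that, for the reasons in the count check above. One narrow case remains: a related, asymptomatic grade 3 value, left untreated, judged not clinically significant, and found on an unscheduled test during the five dosing days. Glucose is the likelier example, because the grade 3 row of 6.2.2.8 names stopping but no therapy. In that case one event would move the first cohort from none in three (13 patients) to one in three (16 or 10 patients). No probability is attached to it: the protocol bands grade 3/4 metabolic abnormalities from pooled data, not from a 5-day course.

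The conclusion on timing assumes that dosing starts at visit 4. The conclusion on the count assumes that values are treated as Section 6.2.2.8 directs.

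**What to change.** Reconcile Table 6-1 with Section 6.2.2.8 for grade 3 metabolic events, and with Section 6.2.2.6 for grade 2 mucositis, so that each toxicity and grade carries one action wherever it appears. If intolerable grade 2 mucositis is meant as a separate category, say so in both places. Replace the reference to 6.2.3.8 with the correct section number, and correct the two references to 6.2.3.10 in Section 5.1 at the same time. Which action applies is for the sponsor and the investigator to decide.

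The cost is a few words in two or three places. Because the wording governs stopping of treatment, it belongs in an amendment reviewed under Section 10. No change to the escalation rule, the sample size or the analysis follows from this point.

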6.2.2 Management of specific toxicities

Overall, safety data available from completed, controlled and uncontrolled studies indicate that everolimus is generally well tolerated at weekly or daily dose schedules. The safety profile is characterized by manageable adverse events (AEs). These AEs are generally reversible and non-cumulative.

Adverse events most frequently observed with everolimus are stomatitis, rash, fatigue, diarrhea, infections, nausea, decreased appetite, anemia, dysgeusia, pneumonitis, edema peripheral, hyperglycemia, asthenia, pruritus, weight decreased, hypercholesterolemia, epistaxis, cough, and headache. Overall, the most frequently observed laboratory abnormalities include decreased hematology parameters including hemoglobin, lymphocytes, platelets, and neutrophils (or collectively as pancytopenia); increased clinical chemistry parameters including cholesterol, triglycerides, glucose, aspartate transaminases, creatinine, alanine transaminases, and bilirubin; and decreased clinical chemistry parameters including phosphate and potassium. The majority of these AEs have been of mild to moderate severity (NCI CTC grade 1-2).

6.2.2.1 Management of infections

Everolimus has immunosuppressive properties and may predispose patients to bacterial, fungal, viral or protozoal infections, including infections with opportunistic pathogens. Localized and systemic infections, including pneumonia, other bacterial infections, invasive fungal infections, such as aspergillosis or candidiasis and viral infections including reactivation of hepatitis B virus, have been described in patients taking Everolimus. Some of these infections have been severe (e.g. leading to sepsis, respiratory or hepatic failure) and occasionally have had a fatal outcome.

Physicians and patients should be aware of the increased risk of infection with Everolimus. Treat pre-existing infections prior to starting treatment with Everolimus. While taking Everolimus, be vigilant for symptoms and signs of infection; if a diagnosis of infection is made, institute appropriate treatment promptly and consider interruption or discontinuation of Everolimus.

If a diagnosis of invasive systemic fungal infection is made, discontinue Everolimus and treat with appropriate antifungal therapy.

Cases of pneumocystis jirovecii pneumonia (PJP), some with a fatal outcome, have been reported in patients who received everolimus. PJP may be associated with concomitant use of corticosteroids or other immunosuppressive agents. Prophylaxis for PJP should be considered when concomitant use of corticosteroids or other immunosuppressive agents are required.

6.2.2.2 Management of skin toxicity

For patients with grade 1 toxicity, no specific supportive care is usually needed or indicated. Rash must be reported as an AE. Patients with grade 2 or higher toxicity may be treated with the following suggested supportive measures at the discretion of the investigator: oral

minocycline, topical tetracycline, topical clindamycin, topical silver sulfadiazine, diphenhydramine, oral prednisolone (short course), topical corticosteroids, or pimecrolimus.

6.2.2.3 Management of Hypersensitivity reactions

Hypersensitivity reactions manifested by symptoms including, but not limited to, anaphylaxis, dyspnea, flushing, chest pain or angioedema (e.g. swelling of the airways or tongue, with or without respiratory impairment) have been observed with everolimus.

6.2.2.4 Angioedema with concomitant use of angiotensin-converting enzyme (ACE) inhibitors

Patients taking concomitant ACE inhibitor therapy may be at increased risk for angioedema (e.g. swelling of the airways or tongue, with or without respiratory impairment).

6.2.2.5 Renal Failure Events

Cases of renal failure (including acute renal failure), some with fatal outcome, occurred in patients treated with everolimus. Renal function of patients should be monitored particularly where patients have additional risk factors that may further impair renal function.

Elevations of serum creatinine, usually mild, and proteinuria have been reported in patients taking everolimus. Monitoring of renal function, including measurement of blood urea nitrogen (BUN), urinary protein, or serum creatinine, is recommended prior to the start of everolimus therapy and periodically thereafter.

